9.3.6.4 Estimand Strategy for AUC Endpoints

The population level summary will be the difference in estimated mean AUC from baseline to the endpoint of interest between delgocitinib cream and alitretinoin capsules. The AUC endpoints are based on curves that will be fitted on values determined for the corresponding continuous and binary endpoints, as presented in Table 9-2.

Once points have been identified in accordance with estimands strategies, a piecewise line function will be drawn to connects points (f(t)), where t is the time in days from baseline). Baseline value will be set at 0 (zero). For each participant, the area under piecewise line will be determined integrating f(t), as follows:

$$AUC = \int_{t=0}^{t=Week \ 24} f(t) \Delta t$$

The integral will be approximated by the trapezoidal rule.

The differences between treatment group will be analysed using robust ANCOVA model with the AUC or related transformation as dependent variable, and treatment, region, hyperkeratotic/non-hyperkeratotic subtype and baseline value (of the measure of interest), as covariates. Details on robust ANCOVA model will be described in the SAP.

The AUC at participant level (to be implemented as dependent variable in the ANCOVA model) will be determined in accordance with nature of the endpoint of interest, as follows:

- **AUC derived from binary endpoints**, such as the AUC of HECSI-90 from baseline up to Week 24: 1 will be assigned when response is observed and 0 otherwise. The AUC is interpreted as number of days with 90% reduction in HECSI score until Week 24.
- AUC derived from continuous endpoints, such as the AUC of change from baseline in DLQI score up to Week 24: For the sake of interpretability, differences will be analysed with opposite sign to interpret positive area as improvement in scores and negative area as worsening.

When analyses require MI procedures of data, 100 complete datasets will be sampled. For each dataset, piecewise line function will be drawn to connects points and the AUC will be determined. ANCOVA model will be fitted for each dataset with treatment, region, hyperkeratotic/non-hyperkeratotic subtype as covariates. The estimates and standard errors from the analyses will be combined using Rubin's rule to provide the estimate and associated standard error.

Primary Estimand: 'Composite' Strategy

For the primary analysis, observed data and missing data will be handled according to the IEs, as described in Table 9-2.

First Supplementary Estimand: 'Pandemic Modified Composite' Strategy

Observed data and missing data of the corresponding continuous or binary endpoint will be handled according to the IEs, as described in Table 9-2.

All missing or 'treated as missing' data will be imputed using MI assuming MAR within treatment groups. The WOCF or non-response imputation of relevant data points not affected by the COVID-19 pandemic will be applied.

Second Supplementary Estimand: 'Treatment Policy' Strategy

Observed data and missing data of the corresponding continuous or binary endpoint will be handled according to the IEs, as described in Table 9-2.

Missing data at Week 12 and Week 24, independent of the COVID-19 pandemic, will be imputed using MI assuming MAR within 4 groups defined according to treatment group and whether the participant has experienced an IE (independent of the COVID-19 pandemic). For imputation purposes, data available from all participants will be used.

For the endpoint of interest, missing data or 'treated as missing' data due to the COVID-19 pandemic will be imputed using MI assuming MAR within treatment group using data from participants who have not experienced an IE.

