9.3 Statistical Analyses

9.3.1 General Considerations

Significance tests will be 1-sided using the 2.5% significance level. All confidence intervals will be presented with 95% degree of confidence, unless otherwise specified.

An observed-cases approach will be used for tabulations of data by visit (that is, involving only those participants who attended each specific visit).

Categorical data will be summarised using the number and percentage of participants in each category. Continuous data will be summarised using the mean, median, SD, 1st quartile, 3rd quartile, minimum, and maximum values.

Baseline measurements will be defined as the latest available observation at or prior to the date of randomisation.

The statistical analyses were performed using SAS software (SAS Institute, Cary NC), version 9.3 or later.

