discontinuation of IMP related to the COVID-19 pandemic	Missing	Non-response	MI (MAR)	MI (MAR)	WOCF	MI (MAR)	MI (MAR)	
No intercurrent events	Observed	Value will be used as observed	Value will be used as observed	Value will be used as observed	Value will be used as observed	Value will be used as observed	Value will be used as observed	
	Missing independent of the COVID-19 pandemic	Non-response	Non-response	MI (MAR)	WOCF	WOCF	MI (MAR)	
	Missing related to the COVID-19 pandemic	Non-response	MI (MAR)	MI (MAR)	WOCF	MI (MAR)	MI (MAR)	

IMP=investigational medicinal product; MAR=missing at random; MI=multiple imputation; WOCF=worst observation carried forward (including baseline value).

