9.5 Sample Size Determination

Approximately 510 participants will be randomly assigned to trial treatment in a 1:1 ratio, with 255 evaluable participants per treatment group. Approximately 660 participants will be screened to achieve this target.

With 510 participants randomised, the trial will provide 80% power to establish superiority of delgocitinib cream with regard to change from baseline to Week 12 in HECSI based on a 1-sided hypothesis test at a 2.5% significance level, assuming a difference in the mean change from baseline to Week 12 in HECSI of 7.5 (with a standard deviation of 30) between the 2 treatment arms (Ruzicka et al, 2008). Since there is limited published data on alitretinoin in terms of HECSI, anticipated treatment difference between delgocitinib and alitretinoin has been set using IGA scales as a surrogate endpoint (LP0133-1273 trial). Expected standard deviation is based on data observed in LP0133-1273 trial.

10 Supporting Documentation and Operational Considerations

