10.5 Appendix 5: COVID-19 Pandemic Contingency Plan

Without compromising the safety of participants and trial integrity, it is expected that efforts are made to secure attendance at sites for all visits, ensuring important efficacy and safety assessments for the trial

If on-site visits are not possible due to local authority-issued preventive measures, the affected site will postpone screening and randomisation of new participants until on-site visits can be conducted. For already randomised participants, post-baseline visits can be done remotely via phone or video. At phone/video visits, no investigator assessments of efficacy can be done, but the following data will be collected remotely, according to the SoA (Table 1-1):

- AE reporting.
- Treatment compliance (daily completion in the eDiary).
- Concomitant medication and concurrent procedures.
- HESD (daily completion in the eDiary).
- Participant assessment of local tolerability (weekly completion in the eDiary).
- PROs (DLQI, HEIS, EQ-5D-5L, TSQM, WPAI-CHE, PGI-S, and PGI-C). The participants will receive a link to complete the PROs in a web browser from their own device.
- New CHE lesions.
- Urine pregnancy test. Women of childbearing potential will receive 1 extra urine pregnancy test at the randomisation visit to keep at home in case on-site visits become impossible during the trial. The participant will perform the test at home and inform the investigator about the result via phone and to send a picture of the test to the site or show it via video. Additional urine pregnancy tests can be shipped to the participant's home together with IMP (see below) if needed.
- For participants treated with alitretinoin:
 - Serum cholesterol and serum triglycerides (fasting values) should continue to be monitored by a local laboratory, at the timepoints outlined in the SoA (Table 1-1).
 - Remote consultation to allow for adequate monitoring of mental health should be maintained at the timepoints outlined in the SoA (Table 1-1). The potential for psychiatric disorders may be increased by COVID-19 isolation measures and this may complicate the clinical picture.

In the eCRF, it will be recorded whether a visit or a given assessment was done remotely or not done. If not done, it will be recorded if this was due to the COVID-19 pandemic.

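### In the AUC of HECSI-90, the primary estimand scores a gap between two observed responses as non-response, at a cost of up to 28 of 164.5 nominal days per missed assessment

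*Combined protocol and SAP*

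**What the plan says.** Section 9.3.6.4 takes the points of each AUC curve from "curves that will be fitted on values determined for the corresponding continuous and binary endpoints, as presented in Table 9-2". It joins them by straight lines, starts the curve at zero and integrates by the trapezoidal rule. For HECSI-90 a visit counts one if response is observed and zero otherwise. The plan then gives the result a meaning: "The AUC is interpreted as number of days with 90% reduction in HECSI score until Week 24".

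Table 9-2 (Section 9.3.6.1) has a block for participants without intercurrent events. In the row "Missing independent of the COVID-19 pandemic", the composite column gives non-response for binary endpoints and WOCF, with baseline among the candidate values, for continuous ones. The row for COVID-related gaps gives the same under the composite strategy. Neither row makes an exception for a gap between two observed visits.

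Section 9.3.8 bases the confirmatory key secondary tests on this estimand. The AUC of HECSI-90 is fifth and the AUC of DLQI change is sixth in the key secondary sequence of Figure 9-1.

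Appendix 5 (Section 10.5) allows remote visits when local preventive measures rule out attendance, and adds: "At phone/video visits, no investigator assessments of efficacy can be done". HECSI is therefore missing at a remote visit. The same appendix lists DLQI among the data still collected, through a web link.

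**The concern.** The composite strategy treats an intercurrent event as treatment failure. Section 9.3.6.1 names those events: rescue treatment and permanent discontinuation of IMP. A missed assessment in a participant who has had neither is not among them, so scoring it as failure is a missing-data rule and not part of the estimand.

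At a single time point such a rule costs one response. In an AUC it also pulls down the line on both sides of the gap. A participant seen in response before and after is charged about four weeks of non-response, and the result can no longer be read as days in response.

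Two key secondary endpoints are at stake. Attenuation makes the fifth test harder to pass, and a failure there stops the tests that follow it. If the arms miss visits at different rates, attendance is counted as efficacy. Participants know their treatment, so different rates are possible.

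**Working it through.** **The plan's own figure.** The documents give no number for the AUC endpoints. The only sizing is for the primary endpoint: one-sided 2.5%, difference 7.5, SD 30, 80% power.
- n per arm = 2 × (1.960 + 0.842)² × (30/7.5)² ≈ 251.2, so 252 per arm and 504 in total, against 510 planned.
- Power with 255 per arm = Φ(7.5/(30 × √(2/255)) − 1.96) = 80.6%.

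The stated size is reproduced. The 255 per arm is used again in step 4.

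**1. Maximum AUC.** The Schedule of Activities has visits on days 1, 8, 15, 29, 57, 85, 113, 141 and 169, so t = 0, 7, 14, 28, 56, 84, 112, 140 and 168. With f(0) = 0 and f = 1 from Week 1, AUC = 168 − 7/2 = 164.5 days.

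**2. Loss from one missing HECSI scored zero.** For an interior visit i the loss is (t(i+1) − t(i−1))/2. For the last visit it is half the final interval.

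| Missing visit | Loss (days) | Share of 164.5 |
|---|---|---|
| Week 1 | (14 − 0)/2 = 7 | 4.3% |
| Week 2 | (28 − 7)/2 = 10.5 | 6.4% |
| Week 4 | (56 − 14)/2 = 21 | 12.8% |
| Week 8, 12, 16 or 20 | 56/2 = 28 | 17.0% |
| Week 24 | (168 − 140)/2 = 14 | 8.5% |

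Week 1 follows the zero baseline and Week 24 has no later visit, so neither lies between two observed responses. If actual days are used, the ±3-day windows allow neighbours 62 days apart and a loss of 31. Two consecutive missing visits among Weeks 8 to 20 cost 56 days. The share is larger in later responders: 28 of 126 (22%) with response from Week 8, and 28 of 98 (29%) with response from Week 12.

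**3. DLQI AUC.** The unit is point-days. With an assumed constant improvement of d points, the full area is 164.5 × d. One DLQI not completed at Week 8, 12, 16 or 20 is carried back at least to baseline, which costs 28 × d: 140 of 822.5 for d = 5 and 280 of 1645 for d = 10, 17% in each case. If an earlier value was 3 points worse than baseline (assumed), the loss is 28 × (d + 3), or 224 and 364 point-days.

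**4. Effect on the comparison (HECSI-90).** The trapezoid is linear in the visit values and baseline is zero. A per-visit missing rate m unrelated to response therefore turns the mean AUC into (1 − m) × mean. For a full responder, m = 2%, 5% and 10% (assumed) cost 3.3, 8.2 and 16.5 days. If both arms share the same m, the treatment difference shrinks by the factor (1 − m). If the true means are equal but the rates differ, the bias is the difference in rates times the mean.

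Illustration only, with an assumed mean of 40 days, an assumed SD of 53 days and a normal approximation: SE = 53 × √(2/255) = 4.69 days. The one-sided error is 1 − Φ(1.96 − bias/SE), with the bias counted positive when it favours delgocitinib.

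| Excess of missed visits | Bias (days) | Bias/SE | One-sided error |
|---|---|---|---|
| 1 point, alitretinoin | 0.4 | 0.09 | 3.0% |
| 2 points, alitretinoin | 0.8 | 0.17 | 3.7% |
| 4 points, alitretinoin | 1.6 | 0.34 | 5.3% |
| 4 points, delgocitinib | −1.6 | −0.34 | 1.1% |

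**The case against.** **The rule is prespecified and coherent.** Non-response for every gap matches the handling of the Week 12 binary endpoints. That is true, but consistency with a single-visit endpoint does not make the AUC mean what Section 9.3.6.4 says it means.

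**Checks exist.** The treatment policy estimand uses multiple imputation for all gaps, and the pandemic modified composite does so for COVID-related ones, which should include remote visits. Section 9.3.6.3 also plans a sensitivity analysis that imputes missing alitretinoin data under MAR and leaves delgocitinib at non-response, with HECSI-90 up to Week 24 as its example. So a reader should not infer that nothing in the plan addresses these gaps. Yet none of these isolates the issue. Treatment policy also changes the handling of intercurrent events, and its detailed text for gaps unrelated to COVID-19 names only Weeks 12 and 24. The pandemic estimand keeps non-response for other gaps. Section 9.3.6.4 lists no sensitivity analysis for the AUC.

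**True status at the gap is unknown.** One might call the imputed dip a false relapse. The documents do not support that. The disease relapses, and stopping treatment is recommended at IGA-CHE 0 or 1 after Week 12 (alitretinoin) or Week 16 (delgocitinib). A real relapse in a later gap is possible.

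**Joining neighbours has its own error.** A true response–relapse–response pattern would gain 28 days. A participant who responds only at Week 24 has an AUC of 14 days, and missing Week 20 would make it 28. This stands as a cost, but it does not run systematically in one direction.

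**The SAP may already deal with it.** Section 9 defers technical detail to the SAP, and the combined document holds no separate SAP text. A rule or added analysis for intermittent gaps cannot be excluded.

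**Conclusion.** The point holds for the AUC of HECSI-90 under the primary composite estimand. A gap without an intercurrent event is scored as non-response between two observed responses, at a cost of 28 of 164.5 nominal days at Week 8, 12, 16 or 20 and 21 days at Week 4. That conflicts with the plan's own reading of the endpoint. The day counts rest only on the visit schedule and the trapezoid.

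Two stronger readings are not supported:
- **That remote visits damage both key AUC endpoints, or that 28 of 164.5 applies to both.** DLQI is collected remotely and its AUC is in point-days, so it is affected only when the questionnaire is not completed. The exploratory HESD AUCs come from the home eDiary, which is also kept during remote periods.
- **That the error rate rises to about 5%.** This needs an assumed 4-point excess of missed visits on alitretinoin together with the assumed mean and SD. The same excess on delgocitinib gives about 1.1%. The documents give no missed-visit rates by arm, and the planned test is a robust ANCOVA, possibly on a transformed AUC. The direction of any bias is therefore undetermined, and for the same reason the rule cannot be called conservative.

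Section 9.3.2 also says that COVID-related missing data will be imputed under MAR without naming an estimand, whereas the composite column of Table 9-2 gives non-response or WOCF. The two need to agree.

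This is a cheap improvement worth making. It does not touch the primary endpoint or its sample size.

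**What to change.** In Section 9.3.6.4 and Table 9-2, add for the AUC endpoints: in participants without an intercurrent event, a missing value between two observed visits is not imputed, and the line joins the adjacent observed values. Non-response or WOCF continues to apply after an intercurrent event and after the last observed visit. Keep the present rule as a sensitivity analysis, so that the effect of the choice is visible.

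Under this rule a full responder with one gap at Week 8 to 20 goes from 136.5 back to 164.5 days.

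State in Section 9.3.2 which estimands its MAR sentence covers, in line with Table 9-2.

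The cost is a few sentences and one extra run. Section 9 allows the SAP to be revised before database lock. The downside to record is that a real relapse at the missed visit is smoothed over and that a gap between non-response and response earns partial credit. If the SAP already contains such a rule, the sponsor need only confirm it.

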1.1 Synopsis

Protocol Title: A 24-week, randomised, assessor-blinded, active-controlled, parallel-group, phase 3, 2-arm trial to compare the efficacy and safety of delgocitinib cream 20 mg/g twice-daily with alitretinoin capsules once-daily in adult participants with severe chronic hand eczema

Brief Title: A 24-week trial to compare the efficacy and safety of delgocitinib cream 20 mg/g twice-daily with alitretinoin capsules once-daily in adult participants with severe chronic hand eczema

Sponsor Protocol No.: LP0133-1528

Trial Phase: Phase 3

Sponsor: LEO Pharma A/S

Rationale: There is a clear unmet need for long-term treatment options for patients suffering from moderate to severe chronic hand eczema (CHE). Alitretinoin is the only approved product specifically indicated for treatment of CHE, but it is only indicated for severe CHE and only approved in few countries worldwide. Delgocitinib cream has the potential to become an effective, well-tolerated, and user-friendly treatment for CHE and thereby improve the everyday lives of affected patients. The purpose of this 24-week trial is to compare efficacy, health-related quality of life, and safety of delgocitinib cream and alitretinoin capsules in participants diagnosed with severe CHE.

Objectives and Endpoints and/or Estimands:

Primary Objective

Objectives	Estimand type and strategy	Endpoints
Primary objective: To compare the efficacy and health-related quality of life of twice-daily topical application of delgocitinib cream with once-daily oral administration of alitretinoin capsules in the treatment of patients with severe CHE.	Primary. 'Composite' strategy. First supplementary. 'Pandemic modified composite' strategy. Second supplementary (for endpoints at Week 12 and Week 24). 'Treatment policy' strategy.	 Primary endpoint: Change in HECSI score from baseline to Week 12. Key secondary endpoints: HECSI-90 at Week 12. IGA-CHE TS at Week 12. Change in HESD itch score (weekly average) from baseline to Week 12. Change in HESD pain score (weekly average) from baseline to Week 12. AUC of HECSI-90 from baseline up to Week 24. AUC of change from baseline in DLQI score up to Week 24. Change in HECSI score from baseline to Week 24.

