9.3.6 Estimand Strategy

9.3.6.1 General Considerations

The analysis of endpoints related to efficacy and health-related quality of life will be based on the FAS.

The following primary and supplementary estimands will be defined for binary, continuous, and AUC endpoints (primary and key secondary endpoints):

- The primary estimand will use a 'composite' strategy to handle IEs. With a 'composite' strategy, the occurrence of an IEs is a component of the endpoint. The occurrence of any IE will lead to assume failure of the randomised treatment. For continuous endpoints, observed data after the IEs will be imputed as non-response by using WOCF (including baseline value) which is considered an extremely unfavourable value.
- A first supplementary estimand will use a 'pandemic modified composite' strategy. The strategy follows a 'composite' strategy for IEs independent of the COVID-19 pandemic. However, data collected after the IE related to the COVID-19 pandemic will be 'treated as missing' and imputed assuming MAR.
- A second supplementary estimand will use a 'treatment policy' strategy which attempts to quantify the effect of the randomised treatment, ignoring the occurrence of IEs. This policy reflects the intention-to-treat (ITT) principle and is intended to measure the effectiveness of the treatment under conditions closer to 'real world' conditions where patients will not adhere perfectly to the protocol when taking medication. Data collected for the endpoint of interest are used regardless of whether an IE occurred, except for the occurrence permanent discontinuation of IMP related to the COVID-19 pandemic data which will be assumed MAR and imputed.

To support the 'treatment policy' strategy, participants who experience IEs prior to Week 12 will be asked to attend the primary endpoint visit at Week 12 and nominal visit at Week 24 for collection of data. Participants who experience IEs between Week 12 and Week 24 will be asked to attend the nominal visit at Week 24 for collection of data.

For primary and key secondary endpoints only, pre-specified sensitivity analyses will also be conducted for selected combinations of endpoints and estimands to assess the robustness of the results with respect to the handling of missing data.

Analysis to summarise and assess the effect of patterns of missing data related to the COVID-19 pandemic will be specified in the SAP prior to DBL.

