9.3.6.2 Estimand Strategy for Continuous Endpoints

The population level summary will be the difference in mean change (or percentage change) from baseline to the endpoint of interest between delgocitinib cream and alitretinoin capsules.

The change (or percentage change) from baseline to the endpoint of interest will be analysed using an analysis of covariance (ANCOVA) model with effects of treatment group, region, hyperkeratotic/non-hyperkeratotic subtype, and baseline value (of the measure of interest).

When analyses require multiple imputation (MI) procedures of data, 100 complete datasets will be sampled. For each dataset, the ANCOVA model will be fitted. The estimates and standard errors from the analyses will be combined using Rubin's rule to provide the estimate and associated standard error.

Primary Estimand: 'Composite' Strategy

For the primary analysis, observed and missing data will be handled according to the IEs, as described in Table 9-2.

For the sensitivity analysis, which is rather conservative against the delgocitinib group, missing data at the endpoint of interest, for participants who did not experience IEs prior to that, will be handled as follows:

- For participants in the delgocitinib cream group, missing data will be imputed as WOCF (including baseline value).
- For participants in the alitretinoin capsules group, missing data will be imputed using MI assuming MAR.

First Supplementary Estimand: 'Pandemic Modified Composite' Strategy

Observed and missing data will be handled according to the IE, as described in Table 9-2.

All missing or 'treated as missing' data will be imputed using MI assuming MAR within treatment groups. The WOCF imputation of relevant data points not affected by the COVID-19 pandemic will be applied.

Second Supplementary Estimand: 'Treatment Policy' Strategy

Observed data and missing data will be handled according to the IEs, as described in Table 9-2.

Missing data at Week 12 and Week 24, independent of the COVID-19 pandemic, will be imputed using MI assuming MAR within 4 groups defined according to treatment group and whether the participant has experienced an IE (independent of the COVID-19 pandemic). For imputation purposes, data available from all participants will be used.

For the endpoint of interest, missing data or 'treated as missing' data due to the COVID-19 pandemic will be imputed using MI assuming MAR within treatment group using data from participants who have not experienced an IE.

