9.3.9 Exploratory Endpoints Analysis

The analysis of exploratory endpoints will be based on the FAS.

The analysis of exploratory endpoints will resemble the primary analysis for the primary estimand related to a specific endpoint type: binary, continuous, or AUC. For details refer to Section 9.3.6.

Table 9-4 provides an overview of the statistical analysis of the exploratory endpoints.

Table 9-4 Overview of the Statistical Analysis of Exploratory Endpoints

Endpoints	Type of	Primary estimand					
	endpoint	Strategy to handle IEs	Handling of missing data and data collected after IE				
Effica	асу						
IGA-CHE TS at Week 24.	Binary	Composite	Non-response imputation				
HECSI-75 at Week 12 and Week 24.							
HECSI-90 at Week 24.							
Reduction of HESD itch score (weekly average) of ≥3 points ¹ at Week 12 and Week 24.							
Reduction of HESD itch score (weekly average) of ≥4 points ² at Week 12 and Week 24.							
Reduction of HESD pain score (weekly average) of \geq 3 points ³ at Week 12 and Week 24.							
Reduction of HESD pain score (weekly average) of ≥4 points ⁴ at Week 12 and Week 24.							
Reduction of HESD score (weekly average) of ≥3 points ⁵ at Week 12 and Week 24.							
Reduction of HESD score (weekly average) of ≥4 points ⁶ at Week 12 and Week 24.							
Change in HESD itch score (weekly average) from baseline to Week 24.	Continuous	Composite	WOCF (including baseline value)				
Change in HESD pain score (weekly average) from baseline to Week 24.							
Change in HESD score (weekly average) from baseline to Week 12 and Week 24.							
AUC from baseline to Week 24 of reduction of HESD itch score (weekly average) of ≥3 points ¹	AUC (derived	Composite	Non-response imputation				
AUC from baseline to Week 24 of reduction of HESD itch score (weekly average) of ≥4 points ²	from binary)						
AUC from baseline to Week 24 of reduction of HESD pain score (weekly average) of ≥3 points ³							
AUC from baseline to Week 24 of reduction of HESD pain score (weekly average) of ≥4 points ⁴							
Health-related quality of life							
Change in DLQI score from baseline to Week 12 and Week 24.	Continuous	Composite	WOCF (including baseline value)				
Change in HEIS (individual domains and total score) from baseline to Week 12 and Week 24.							
Change in EQ-5D-5L index score from baseline to Week 12 and Week 24.							
Change in EQ-5D-5L visual analogue scale score from baseline to Week 12 and Week 24.							

Endpoints	Type of	Primary estimand		

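### Section 9.3.6.4: the ANCOVA fitted to each imputed AUC dataset omits the baseline covariate that the main AUC model includes

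*Combined protocol and SAP*

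**What the plan says.** Section 9.3.6.4 (AUC endpoints) first defines a robust ANCOVA of the AUC, or a transformation of it, on treatment, region, "hyperkeratotic/non-hyperkeratotic subtype and baseline value (of the measure of interest), as covariates". It adds: "Details on robust ANCOVA model will be described in the SAP". Later, for analyses that need MI with 100 completed datasets, it says: "ANCOVA model will be fitted for each dataset with treatment, region, hyperkeratotic/non-hyperkeratotic subtype as covariates". That second list has no baseline term, and the word robust is also gone.

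Section 9.3.6.2 (continuous endpoints) defines its ANCOVA with "effects of treatment group, region, hyperkeratotic/non-hyperkeratotic subtype, and baseline value (of the measure of interest"). Its MI step then reads only: "For each dataset, the ANCOVA model will be fitted". That points back to the model already defined, so baseline stays in. Section 9.3.6.3 (binary endpoints) likewise repeats the same two stratification factors under MI.

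On the scope of the treatment-policy estimand, the synopsis and Table 3-1 say "Second supplementary (for endpoints at Week 12 and Week 24"), while Section 9.3.6.1 says "The following primary and supplementary estimands will be defined for binary, continuous, and AUC endpoints (primary and key secondary endpoints"). Section 9.3.6.4 and Table 9-3 then apply treatment policy to the AUC endpoints.

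**The concern.** A programmer who follows the MI sentence literally would leave baseline out of every AUC analysis that uses imputed data. Two things are then at stake.

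The first is comparability. The supplementary estimands are there to show what changes when intercurrent events are handled differently. If the covariate set changes as well, a gap between the primary and supplementary AUC results cannot be put down to the estimand alone.

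The second is precision. The AUC of change from baseline in DLQI contains the baseline score itself, so it will usually be correlated with baseline. Without that term the analysis becomes an unadjusted comparison of change scores, and chance baseline imbalance is not corrected. HECSI-90 is already defined relative to each participant's baseline, so less is lost there, possibly almost nothing.

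**Working it through.** **Which analyses are reached.** Table 9-2 uses non-response or WOCF in every composite cell, so the primary AUC analyses need no MI, and Section 9.3.8 bases the confirmatory tests on those. For the exploratory AUC endpoints, Section 9.3.9 says "The analysis of exploratory endpoints will resemble the primary analysis for the primary estimand", so they need none either. MI enters the AUC endpoints through the pandemic-modified composite, through treatment policy where it is applied to AUC, and through any MI-based AUC sensitivity analysis.

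**The plan's own sample size.** Inputs from Section 9.5: difference 7.5, SD 30, 1-sided 2.5%, power 80%. Per arm, n = 2 × (30/7.5)² × (1.960 + 0.842)² ≈ 251.2, so 252 per arm and 504 in total. At 255 per arm the power is 80.6%. The stated 510 reproduces. It rests on the Week 12 HECSI change, so the AUC model does not enter it.

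**Why DLQI AUC is tied to baseline.** The scheduled visits fall on days 0, 7, 14, 28, 56, 84, 112, 140 and 168 from baseline. The trapezoid weights are 3.5, 7, 10.5, 21, 28, 28, 28, 28 and 14, which sum to 168. The change at day 0 is zero, so the post-baseline weights sum to 168 − 3.5 = 164.5, and

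AUC of change = Σ wₖYₖ − 164.5 × Y₀.

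The baseline score therefore enters directly. Every curve starts at zero, so the starting point itself carries no baseline information. The plan reverses the sign for analysis, which does not affect ρ².

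*One illustration, with assumed inputs:* equal SD at all visits, correlation 0.5 between baseline and later visits, and 0.7 among later visits. With uₖ = wₖ/164.5, Σuₖ² = 3932.25/27060.25 = 0.1453. In units of 164.5 baseline SDs:
- variance = 0.1453 + 0.8547 × 0.7 + 1 − 2 × 0.5 = 0.7436
- covariance with Y₀ = 0.5 − 1 = −0.5
- ρ = −0.5/√0.7436 = −0.58
- variance factor = 1/(1 − 0.336) = 1.51

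**Cost of leaving baseline out, by assumed ρ.** In a linear complete-data model the variance factor is 1/(1 − ρ²) and the SE factor is its square root. The last column is the SD of the shift in the estimate caused by the covariate change alone, ρ√(4/510), divided by the adjusted SE, √(1 − ρ²)·√(4/510). It reduces to ρ/√(1 − ρ²).

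| assumed ρ | variance factor | SE factor | shift / adjusted SE |
|---|---|---|---|
| 0.1 | 1.01 | 1.005 | 0.10 |
| 0.3 | 1.10 | 1.05 | 0.31 |
| 0.5 | 1.33 | 1.15 | 0.58 |
| 0.7 | 1.96 | 1.40 | 0.98 |

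**Simulation check.** Setting: 510 participants, 1:1 allocation, 2,000 runs per setting, ordinary ANCOVA on complete data, true effect 0.25 SD, ρ of 0.3, 0.5 and 0.7.
- Mean estimates were 0.248–0.256 without baseline and 0.251–0.255 with it.
- SEs were 0.0885 without baseline, against 0.0845, 0.0767 and 0.0632 with it.
- Under no effect, 1-sided rejection was 1.9%–2.7%. The Monte Carlo SE is √(0.025 × 0.975/2000) ≈ 0.35 percentage points, so this is consistent with 2.5%.

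**The case against.** The best defence is that Section 9.3.6.4 defines one AUC model, with baseline, and that the MI sentence is a loose restatement of it. Section 9 calls itself a summary and leaves the detail of the robust ANCOVA to the SAP. This has force: a drafting slip is the likelier explanation, and a reader who infers that the analyses will in fact be run without baseline goes further than the text allows. It does not remove the point. Unlike Section 9.3.6.2, the sentence gives its own, shorter list. The document reviewed contains no separate SAP text, so the deferral cannot be shown to settle the matter.

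A second objection is that the figures do not describe the planned analysis. That stands. Every correlation is assumed. The model is to be robust, possibly on a transformed AUC, and the reference list includes a paper on rank-transformed covariance analysis. WOCF and between-imputation variance are ignored, and the latter would dilute the effect. The table shows direction and plausible range only, and it should not be turned into a number of participants lost.

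Three stronger readings are tempting and not supported:
- **A threat to the confirmatory AUC tests.** The composite analyses use no MI.
- **No rule for intermediate AUC visits under treatment policy.** Table 9-2 assigns MI under MAR with no visit limit. The instruction to use data from all participants reads naturally as a contrast with the pandemic rule, which uses only participants without an intercurrent event. More detail would help, but this is not a contradiction.
- **A firm count of affected analyses.** The MI-based sensitivity analysis in Section 9.3.6.3 takes HECSI-90 over the period to Week 24 as its example, so the reach may exceed the supplementary estimands.

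**Conclusion.** The mismatch is real and can be read within one section. It is minor. As written, MI-based AUC analyses would use a different covariate set from the primary AUC analysis. They would lose precision, and comparison with the primary result would be muddied, chiefly for the AUC of DLQI change. The documents give no correlation from which to size the loss. It ranges from negligible at ρ near 0.1 to roughly a doubling of variance at ρ = 0.7, under a linear complete-data model that only approximates the plan. The treatment difference is not biased and false positives do not increase. The confirmatory conclusions do not depend on it.

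The difference in treatment-policy scope between the synopsis and Table 3-1 on one side and Sections 9.3.6.1 and 9.3.6.4 and Table 9-3 on the other is an editorial matter. An AUC up to Week 24 could even be read as a Week 24 endpoint.

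**What to change.** In the MI sentence of Section 9.3.6.4, state that the same robust ANCOVA as in the main AUC analysis, including the baseline value of the measure, is fitted to each imputed dataset. If a different model is intended, say so and justify it. Align the SAP, which Section 9 allows to be revised before database lock. If the SAP already specifies baseline, only the protocol sentence needs correcting.

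The cost is one phrase and, in a linear model, one degree of freedom. HECSI and DLQI are already scheduled at the baseline visit, so no new data, visits or participants are needed.

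As an editorial change at the same time, make the treatment-policy scope in the synopsis and Table 3-1 agree with Sections 9.3.6.1 and 9.3.6.4 and Table 9-3.
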